6. BASELINE, EXPOSURE, AND DISPOSITION VARIABLES AND ANALYSES

[Appendix A](#) provides a list of planned tables, figures, and listings. Sample data displays are included in a separate document.

6.1. Baseline and Demographics, Physical Characteristics, and Disease History

6.1.1. Demographics

The following demographics will be summarized and listed for the ITT population during the VC period and the LTS evaluable population during the LTS period: age, age group, sex, race, ethnicity, weight, height, and body mass index.

6.1.2. Baseline Disease Characteristics

The following baseline disease characteristics summarized and listed for the ITT population during the VC period include, but are not limited to the following:

- Time since first onset of AD
- Prior history of asthma (no/yes)
- Prior allergies (food, environmental) (no/yes)
- History of contact dermatitis (no/yes)
- Common complications of AD
- Time since onset of current AD episode
- Prior therapy for AD given in the past 30 days (no/yes)
- Total %BSA involvement in current AD episode
- Facial and/or neck involvement (no/yes) during past episodes
- Number of AD episodes/flare-ups over the last 12 months
- Average duration of episodes/flare-ups over the last 12 months
- Baseline IGA score (2, 3)
- Baseline EASI score
- Baseline Itch NRS score

6.1.3. Prior Therapies for Atopic Dermatitis

Prior therapies for AD, including medication and other types of therapies during the 12 months prior to the screening visit, will be coded using the WHO Drug Dictionary and summarized and listed by treatment group for the ITT population. The type of treatment and reason for discontinuation will be summarized as well. Prior therapies for AD in the past 30 days will be summarized in a similar way.

6.1.4. Medical History

For participants in the ITT population during the VC period, medical history will be summarized and listed by assigned treatment groups. This summary will include the number and percentage of participants with medical history for each body system/organ class as documented in the eCRF.

6.2. Disposition of Participants

The number and percentage of participants who were randomized, who were treated, who completed the VC period, who discontinued study treatment, or who withdrew from the study during the VC period with a primary reason for discontinuation will be summarized and listed for the ITT population during the VC period.

The number and percentage of participants who were treated, who completed the LTS period, who were ongoing treatment during the LTS period, who discontinued study treatment, or who withdrew from the study during the LTS period with a primary reason for discontinuation, will be summarized and listed for the LTS evaluable population in the LTS period.

6.3. Protocol Deviations

In general, the following are important protocol deviations that may significantly affect the primary analysis:

- Missing data for the primary endpoint
- Overall application compliance < 80% during the VC period
- Did not apply any study cream in the VC period
- IGA assessment 14 days out of the target visit date at Week 8 (Day 57 ±7)

Participants with any of the deviations listed above will be excluded from the PP population. Additionally, important protocol deviations, such as those related to inclusion/exclusion criteria, discontinuation criteria, and the use of prohibited concomitant medications, will be reviewed. Decisions as to whether any of these deviations warrant exclusion from the PP population will be made prior to unblinding.

Protocol deviations will be summarized and listed by treatment groups in the VC and LTS periods separately.

6.4. Exposure

For participants in the safety population during the VC period and in the LTS evaluable population in the LTS period, descriptive statistics will be provided (ie, by treatment group for the duration of treatment, the average daily amount of cream applied [g], and the total amount of cream applied [g]). Duration of treatment with ruxolitinib cream or vehicle cream is defined as the number of days from Day 1 to the last record of ruxolitinib cream or vehicle cream application in the specific period.

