** Treatment is ceased 3 days after clearing of AD lesions. Treatment is restarted if AD lesions recur. There is no limit on the number of treatment cycles during the 44-week LTS.

Table 3: Schedule of Activities: Vehicle-Controlled Period

Visit Day (Range)	Screening	VC Period				Notes and Protocol Section
	Days -28 (+ 7 ^a) to -1	Day 1/ Baseline	Wk 2 (± 3 d)	Wk 4 (± 3 d)	Wk 8 ^b /ET (± 3 d)	
Administrative procedures						
Informed consent/assent	X					Section 8.1.1.
Contact IRT	X	X	X	X	X	Section 8.1.3.
Inclusion/exclusion criteria	X	X				Section 5.
Demography and general medical history	X*					Section 8.1.5.1. *Height and weight of both parents, if available, should be obtained and entered into the EDC.
Relevant AD medical and treatment history	X					Section 8.1.5.2.
Collect/obtain growth measurements for the year prior to study entry	X*	X*				Section 8.4.3. *Collected at either screening or baseline. A reasonable effort must be made to collect and document measurements prior to baseline. If unable to obtain, the reason should be documented.
Prior/concomitant medications and procedures	X	X	X	X	X	Section 6.6.
Apply study cream at site		X	X	X	X*	Section 6.1; at each visit (except for the Week 8 visit if IGA is 0), starting at Day 1, the participant should apply the first (morning) application under direct site staff supervision to all areas identified at Day 1, even if the AD lesion is cleared or disappeared. *Not applicable to the ET visit.
Weigh and dispense study cream; dispense diary cards		X	X	X	X*	Section 6.1 and Section 8.1.4. * Not applicable to the Week 8 visit if IGA score = 0 or to the ET visit.
Collect and weigh study cream; collect diary cards			X	X	X	Section 6.1.
Assess compliance			X	X	X	Section 6.4.
Safety assessments						
AE assessment	X	X	X	X	X	Section 8.4.1.
Comprehensive physical examination	X				X*	Section 8.4.2.1. *For the ET visit only.

Table 3: Schedule of Activities: Vehicle-Controlled Period (Continued)

Visit Day (Range)	Screening	VC Period				Notes and Protocol Section
	Days -28 (+ 7 ^a) to -1	Day 1/ Baseline	Wk 2 (± 3 d)	Wk 4 (± 3 d)	Wk 8 ^b /ET (± 3 d)	
Safety assessments (continued)						
Targeted physical examination*		X	X	X	X†	
Section 8.4.2.2.
 
*Conducted only when indicated by symptoms reported by participant (ie, AEs or other findings); clinically significant abnormalities (in the investigator's judgment) are to be reported as AEs.
 
†Not done for the ET visit.

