4. STUDY DESIGN

4.1. Overall Design

This is a randomized, double-blind, VC study with an LTS period in pediatric participants with AD eligible for topical therapy, to be conducted at approximately 60 sites in the United States and Canada. For participants who meet all study inclusion criteria and none of the exclusion criteria, study cream will be assigned at the Day 1/baseline visit. Participants will be randomized 2:2:1 to blinded treatment with ruxolitinib cream 0.75% BID, ruxolitinib cream 1.5% BID, or vehicle cream BID, with stratification by baseline IGA score and age. Enrollment will be capped such that no more than approximately 25% of randomized participants have a baseline IGA score of 2. At least 40% of the overall study population will consist of children aged \geq 2 years to 6 years.

During the 8-week VC period, participants will apply study treatment BID to all areas identified for treatment at the Day 1/baseline visit even if the AD begins to improve and lesions decrease in size. Note: Throughout this protocol, the term "participant" refers either to the participants themselves or, in the case of younger children, their parent or legal guardian.

At Week 8, efficacy (the primary endpoint of the study) will be evaluated as the proportion of participants achieving treatment success (IGA score of 0 or 1 with \geq 2-grade improvement from baseline).

Participants who complete Week 8 assessments with no additional safety concerns will continue into the 44-week LTS period with the same treatment regimen, except those initially randomized to vehicle cream will be rerandomized (1:1) in a blinded manner to 1 of the 2 active treatment groups (ruxolitinib cream 0.75% or 1.5% BID). The IGA score required for participants to enter the LTS period is 0 to 4, and participants must have a %BSA in the range of 0% to 20% (excluding the scalp).

During the LTS period, participants will have study visits every 4 weeks until the end of the study (52 weeks total). At each of these visits, including Week 8 (baseline visit for the LTS period), the participant's AD lesions will be evaluated by the investigator to determine whether the participant requires continuation of treatment or should (re)enter an observation/no treatment cycle. If the IGA score is \geq 1, the participant will start or continue active treatment with ruxolitinib cream (0.75% or 1.5%) BID. If the IGA score is 0 (clear), the participant will (re)enter an observation/no treatment cycle.

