The start and end dates of treatment applications will be captured by the participant. Once the lesions clear, participants should continue to apply study cream for an additional 3 days to the areas of the body where lesions were last present before discontinuing treatment. If this 3-day window is during a study visit and the IGA score is 0, as assessed by the investigator, treatment is to be stopped. The date of the study visit will be recorded as the treatment cycle end date. If a lesion recurs, then treatment should be resumed at the first sign of recurrence.

At any time during the LTS period, if a participant's new areas to be treated in addition to the areas identified at the previous visit exceed 20% BSA, then the participant should be discontinued from study treatment and complete the EOT assessments.

No study treatment adjustments are allowed except for temporary drug discontinuation, if needed (eg, for management of an AE; see Section 6.5).

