3. STUDY DESIGN

[figure not shown]
This is a randomized, double-blind, VC study with an LTS period in pediatric participants aged ≥ 2 to < 12 years with AD eligible for topical therapy. For participants who meet all study inclusion criteria and none of the exclusion criteria, study drug will be assigned at the Day 1/baseline visit. Participants will be randomized 2:2:1 to blinded treatment with either ruxolitinib 0.75% cream BID, ruxolitinib 1.5% cream BID, or vehicle cream BID, with stratification by baseline IGA score and age. Enrollment will be capped, such that no more than approximately 25% of randomized participants have a baseline IGA score of 2. At least 40% of the overall study population will consist of children aged ≥ 2 to 6 years.

Participants who complete Week 8 assessments with no additional safety concerns will continue into the 44-week LTS period with the same treatment regimen, except those initially randomized to vehicle cream who will be rerandomized (1:1) in a blinded manner to 1 of the 2 active treatment groups (ruxolitinib 0.75% or 1.5% cream BID). The IGA score required for participants to enter the LTS period is 0 to 4, and participants must have a %BSA in the range of 0% to 20% (excluding the scalp).

Following the end of treatment (Week 52/EOT or ET), all participants will have a safety follow-up visit 30 days later (or 30 days after the last application of study treatment if the Week 52/EOT or ET visit was not performed); this visit will evaluate the safety and duration of response (refer to Protocol [Amendment 6](#)).

Figure 1 presents the study design schema.

Figure 1: Study Design Schema

- At Week 8 (LTS baseline), participants initially on vehicle during the VC period will be rerandomized to either ruxolitinib 1.5% or 0.75% cream BID. Participants initially randomized to either ruxolitinib 0.75% or 1.5% BID will continue their treatment through the LTS period.

** Treatment is ceased 3 days after clearing of AD lesions. Treatment is restarted if AD lesions recur. There is no limit on the number of treatment cycles during the 44-week LTS.

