4. DATA HANDLING DEFINITIONS AND CONVENTIONS

4.1. Scheduled Study Evaluations and Study Periods

4.1.1. Day 1

Day 1 is the date that the first application of ruxolitinib cream or vehicle cream is administered to the participants in the specific period.

For randomized participants not treated with any study drug, Day 1 is defined as the day of randomization.

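### For children with two or more LTS treatment cycles, the duration of treatment in SAP 6.4 counts the planned no-treatment days between cycles as days on treatment

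*SAP*

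**What the plan says.** SAP 6.4 (Exposure) covers the safety population in the VC period and the LTS evaluable population in the LTS period. It gives one definition of duration for both: "defined as the number of days from Day 1 to the last record of ruxolitinib cream or vehicle cream application in the specific period". The starting point is set per period in SAP 4.1.1: "Day 1 is the date that the first application of ruxolitinib cream or vehicle cream is administered to the participants in the specific period". No days are subtracted and there is no separate LTS rule. Appendix A assigns LTS exposure to Table 3.1.1.2.

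LTS treatment is intermittent by design. Protocol 4.1 states: "If the IGA score is 0 (clear), the participant will (re)enter an observation/no treatment cycle". Between visits, families stop applying cream 3 days after lesions have gone. Protocol 6.1 adds: "If a lesion recurs, then treatment should be resumed at the first sign of recurrence". The footnote to Figure 1 in SAP section 3 says: "There is no limit on the number of treatment cycles during the 44-week LTS".

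The dates needed to separate treated from untreated time are collected. Protocol 6.1 says: "The start and end dates of treatment applications will be captured by the participant". Protocol 4.1 puts the beginning and end of every cycle in the study database, and Protocol Table 4 has the site record them at each LTS visit.

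**The concern.** A first-to-last span measures treated time only if treatment runs without planned breaks. That holds by design in the VC period, where all areas identified at baseline are treated to Week 8 even if they clear. It does not hold in the LTS period, where the breaks are part of the regimen.

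Protocol 2.3.1 gives the purpose of the LTS period as safety information under intermittent use over a longer time. A reader of Table 3.1.1.2 would take a row called duration of treatment as days on cream, in children aged 2 to under 12. For anyone with repeated cycles that row would be too high, and the error can only go upward or be zero. The other exposure measures do not supply the missing number. Total grams does not convert to days, because the treated area varies, and SAP 6.5 summarizes compliance for the VC period only.

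**Working it through.** The documents state no LTS exposure figure, so there is nothing to reproduce. The check compares two counts on the same cycle dates.

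**Inputs from the documents**
- Span rule: SAP 6.4, with the period-specific Day 1 of SAP 4.1.1.
- LTS length: 44 weeks, so 44 × 7 = 308 days.
- Stop and restart rules and unlimited cycles: Protocol 4.1 and 6.1; SAP section 3.

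**Assumptions**
- The cycle lengths and gaps below are illustrations, because the documents give none.
- Both end days are counted (the +1), following the study-day convention in SAP 4.1.2. SAP 6.4 does not say this itself.

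**Formulas**
- Span (SAP 6.4) = last LTS application day − first LTS application day + 1.
- On-treatment days = sum over cycles of (end day − start day + 1).
- Untreated days counted as treatment = span − on-treatment days, which is the sum of the gaps between cycles.

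**Results** (LTS study days, Day 1 = first LTS application)

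| Assumed pattern | Cycle days | Span | On treatment | Untreated days counted | Ratio |
|---|---|---|---|---|---|
| One 56-day cycle | 1–56 | 56 | 56 | 0 | 1.00 |
| Two cycles, 1-day gap | 1–28, 30–57 | 57 | 56 | 1 | 1.02 |
| Two 28-day cycles, 28-day gap | 1–28, 57–84 | 84 | 56 | 28 | 1.50 |
| Two 28-day cycles, 84-day gap | 1–28, 113–140 | 140 | 56 | 84 | 2.50 |
| Two 28-day cycles, 252-day gap | 1–28, 281–308 | 308 | 56 | 252 | 5.50 |
| Four 28-day cycles, 56-day gaps | 1–28, 85–112, 169–196, 253–280 | 280 | 112 | 168 | 2.50 |

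For the 84-day gap: span = 140 − 1 + 1 = 140; on treatment = 28 + 28 = 56; difference = 84.

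**Where the excess is zero.** Only gaps between the first and last LTS application enter the span. A child who is clear at Week 8 and has one later cycle has a Day 1 at the start of that cycle, so the LTS row is correct. No-treatment time after the last application is also left out.

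**A limit of the alternative count.** Under Protocol Table 4 and Protocol 6.1, if a visit falls in the 3-day window and the IGA score is 0, the visit date becomes the cycle end date. Protocol 6.1.1 says the morning application is not made at home on a visit day, and Table 4 limits application at the site to participants with active lesions. That end date can therefore be a day without cream, and (end − start + 1) would count one day too many for such a cycle.

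**The case against.** The strongest reply is that the span is a defined convention and contradicts nothing. Protocol 6.5 lists clearance of lesions in the LTS period as a cause of temporary interruption, alongside adverse events, and Protocol 8.8 places the end of treatment at Week 52 however many cycles there were. On that usage, a duration that includes interruptions coherently describes an intermittent regimen. The span also fits the way safety events are counted: SAP 9.2.1 runs the treatment-emergent window from the first application in a period to 30 days after the last (or to the first application in the next period), gaps included. Both points stand. They are reasons to keep the span, but not to let it be the only duration reported under a label that reads as treated time.

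Redaction also matters. Parts of the SAP are blacked out and the table shells are in a separate document, so a cycle or treatment-free summary may exist. It would reduce the consequence, but it would not change the definition in SAP 6.4. Participants treated almost continuously would show little or no excess, so the illustrated gaps say nothing about the trial average.

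Three stronger readings are tempting and are not supported:
- **Table 3.1.1.3 (baseline to Week 52) is also overstated.** SAP 6.4 defines duration only within a period. The table could add the two period durations, in which case a gap between the VC period and the first LTS application is not counted.
- **Average daily grams is diluted.** SAP 6.4 names no divisor, so no bias can be shown.
- **Exposure-adjusted event rates are biased.** SAP 9.2.1 names no denominator, so this cannot be shown either.

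**Conclusion.** The point holds for one row of one table. By the definition in SAP 6.4, the LTS duration of treatment for a participant with two or more LTS cycles equals days on cream plus all planned no-treatment days between those cycles. The span is a coherent quantity, but it is ill suited to serve as duration of treatment in a treat and re-treat period.

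The size cannot be computed from the documents. In the assumed patterns with gaps of 28 to 252 days, the reported duration is 1.5 to 5.5 times the days on cream; with a 1-day gap the difference is one day. These ratios describe single hypothetical children and do not estimate the trial mean.

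Participants with one LTS cycle, the VC duration, total grams, event counts and the efficacy results are unaffected. The change is worth making because it is cheap and alters a reported safety-exposure figure. It does not put the trial's conclusions at risk.

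**What to change.** In SAP 6.4, for the LTS period:
- Add on-treatment days, defined as the sum over recorded treatment cycles of (end date − start date + 1). Do not count the end date when it is a study-visit date on which no cream was applied.
- Keep the present measure as a separate row labelled 'time from first to last application'.
- For a baseline-to-Week 52 table, add the VC duration and the LTS on-treatment days.

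No new data are needed. The cost is SAP wording and a little programming. The new measure relies on cycle dates recorded by participants, does not remove missed applications within a cycle, and will make the reported LTS duration smaller.

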6.5. Study Drug Compliance

For participants in the safety population, overall compliance (%) for the application of ruxolitinib cream or vehicle cream during the VC period will be calculated for all participants as follows:

$$\text{Overall application compliance (\%)} = 100 \times [\text{total number of nonmissing applications}] / [\text{total number of intended applications}],$$

where the total number of nonmissing applications is the total number of applications that the participant actually applied during the study and the total number of intended applications is the number of planned applications minus the number of interrupted applications. Overall compliance will be summarized and listed for the safety population during the VC period.

6.6. Prior and Concomitant Therapies

For participants in the ITT population during the VC period, prior and concomitant therapies will be coded using the WHO Drug Dictionary and summarized as number and percentage of participants with prior and concomitant therapies by WHO drug class and WHO drug term.

For participants in the LTS period, only concomitant therapies will be summarized. Concomitant therapies for AD will also be summarized by treatment groups in the VC and LTS periods.

7. EFFICACY

[Appendix A](#) provides a list of planned tables, figures, and listings. Sample data displays are included in a separate document.

7.1. General Considerations

For all continuous variables, both the actual value and change and/or percentage from baseline (if available) will be analyzed.

All by-visit analyses will include the safety follow-up period, if the data are available.

7.2. Analysis of the Primary Efficacy Parameters

7.2.1. Primary Efficacy Measures

7.2.1.1. Investigator's Global Assessment

The IGA is an overall eczema severity rating on a 0 to 4 scale that will be assessed during site visits. The grades for the IGA are shown in [Table 2](#).

Table 2: Investigator's Global Assessment

Grade	Severity	Status
0	Clear	No erythema or induration/papulation, no oozing/crusting; there may be minor residual discoloration.
1	Almost clear	There may be trace faint pink erythema, with almost no induration/papulation, and no oozing/crusting.
2	Mild	There may be faint pink erythema, with mild induration/papulation and no oozing/crusting.
3	Moderate	There may be pink-red erythema with moderate induration/papulation and there may be some oozing/crusting.
4	Severe	There may be deep or bright red erythema with severe induration/papulation and with oozing/crusting.

Source: [FDA 2012](#).

The IGA-TS is defined as an IGA score of 0 or 1 with ≥ 2 -grade improvement from baseline.

7.2.2. Primary Efficacy Analyses

The primary analysis will be based on the ITT population in the VC period. The primary alternative hypothesis (superiority of ruxolitinib 1.5% BID or 0.75% BID compared with vehicle) will be tested using logistic regression. This model will include the treatment group (1.5% BID, 0.75% BID, and vehicle) and stratification factors (baseline IGA score and age). The unadjusted p-values between each treatment group versus vehicle will be calculated based on the Wald test, which will be compared with the procedure defined in Section 3.2. Exact logistic regression ([Mehta and Patel 1995](#)) will be used for all of the comparisons if any of the dose levels have an expected cell count < 5 .

The odds ratio and 95% CI at Week 8 for the response rates (ruxolitinib cream/vehicle) will be computed for the above model. Additionally, the difference in IGA-TS response rates (ruxolitinib cream – vehicle) at Week 8 will be computed. The 95% CI for the difference will be computed based on a large-sample normal approximation with continuity correction.

All nonresponders during the VC period, as well as all participants missing the Week 8 assessment and who discontinue study treatment at any time before Week 8, or discontinue from the study for any reason, will be defined as nonresponders for the nonresponder imputation analysis.

The primary outcome will also be examined for the PP population using the same model as the primary analysis.

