6.5.2. Criteria for Permanent Discontinuation of Study Cream Due to an Adverse Event

The occurrence of unacceptable severity of an AE not caused by the underlying disease will be presumed to be related to study cream and will require that the study cream be permanently discontinued. Unacceptable severity is defined as follows:

- Occurrence of an AE that is related to treatment with the study cream that, in the judgment of the investigator or the sponsor's medical monitor, compromised the participant's ability to continue study-specific procedures or is considered to not be in the participant's best interest.
- Participant presents with a worsening of AD that requires treatment with a prohibited concomitant medication.
- Persistent AE requiring a delay of therapy for more than 2 weeks without resolution of the AE.
- Any Grade 4 laboratory abnormality related to the study cream (see [Table 9](#)).

See Section [7](#) for discontinuation procedures.

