3.3. Sample Size Considerations

Approximately 315 participants will be randomized 2:2:1 to blinded treatment with either ruxolitinib 1.5% cream BID, ruxolitinib 0.75% cream BID, or vehicle cream BID. The sample size calculation is based on the Fisher exact test for the primary efficacy endpoint. Based on the results from the 2 pivotal studies in adolescents and adults with AD (INCB 18424-303 and INCB 18424-304), the response rate of IGA-TS at Week 8 is assumed to be 51% and 47% for the active arms (ie, 1.5% BID and 0.75% BID, respectively) versus 14% for placebo.

Using a 2-sided alpha of 0.025, the sample size will have > 95% power to detect a difference between each of the 2 active treatment groups versus the vehicle. In addition to providing adequate power for efficacy variables, the sample size is determined to provide a large database for safety evaluations.

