APPENDIX A. PLANNED TABLES, FIGURES, AND LISTINGS

This appendix provides a list of the planned tables, figures, and listings for the Clinical Study Report. Shells are provided in a separate document for tables that are not in the most current Standard Safety Tables.

The list of tables, figures, and listings are to be used as guidelines. Modifications of the lists that do not otherwise affect the nature of the analysis will not warrant an amendment to the SAP.

Tables

Table No.	Title	Population	Standard
Baseline Demographic and Characteristic			
1.1.1	Analysis Populations	All	X
1.1.2.1	Summary of Participant Disposition in the VC Period	ITT	X
1.1.2.2	Summary of Participant Disposition in the LTS Period	LTS Evaluable	X
1.1.3	Summary of Number of Participants Enrolled by Country and Site	ITT	X
1.1.4.1	Summary of Protocol Deviations During the VC Period	ITT	X
1.1.4.2	Summary of Protocol Deviations During the LTS Period	LTS Evaluable	X
1.2.1	Summary of Demographics and Baseline Characteristics in the VC Period	ITT	X
1.2.2	Summary of Demographics and Baseline Characteristics in the LTS Period	LTS Evaluable	X
1.3	Summary of Baseline Disease Characteristics	ITT	X
1.4.1	Summary of Prior Non-AD Medications	ITT	X
1.4.2.1	Summary of Prior Therapies for Atopic Dermatitis During the Past 12 Months	ITT	X
1.4.2.2	Summary of Prior Therapies for Atopic Dermatitis During the Past 12 Months by Therapy Type and Discontinuation Reason	ITT	X
1.4.2.3	Summary of Prior Therapies for Atopic Dermatitis During the Past 30 Days	ITT	X
1.4.2.4	Summary of Prior Therapies for Atopic Dermatitis During the Past 30 Days by Therapy Type and Discontinuation Reason	ITT	X
1.4.3.1	Summary of Non-AD Concomitant Medications During the VC Period	ITT	X
1.4.3.2	Summary of Non-AD Concomitant Medications During the LTS Period	LTS Evaluable	X
1.4.3.3	Summary of Concomitant Therapies for AD During the VC Period	ITT	X
1.4.3.4	Summary of Concomitant Therapies for AD During the LTS Period	LTS Evaluable	X
1.5	Summary of General Medical History	ITT	X
1.6.1	Summary of Participants With Assessments Affected by the COVID-19 Pandemic in the VC Period	ITT	X
1.6.2	Summary of Participants With Assessments Affected by the COVID-19 Pandemic in the LTS Period	LTS Evaluable	X

Table No.	Title	Population	Standard
2.2.5.1	Summary of Participants in Each Category of EASI Score in the VC Period	ITT	
Itch NRS Score			

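### A child who uses prohibited atopic dermatitis therapy, stays on study cream and clears by Week 8 counts as a primary-endpoint responder, because no nonresponder rule covers such use

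*SAP*

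**What the plan says.** **Response.** SAP 7.2.1.1 and Protocol 8.2.5 define IGA-TS from the IGA score alone.

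**Nonresponse.** SAP 7.2.2 names observed nonresponders, then children who have no Week 8 assessment and stopped treatment before Week 8, and closes with those who leave the study: "or discontinue from the study for any reason, will be defined as nonresponders for the nonresponder imputation analysis". SAP 4.1.5 makes a missing Week 8 value sufficient. Protocol 10.4.1 makes stopping treatment before the timepoint sufficient, with no condition on missing data. SAP 7.3.2 applies the same imputation to Week 8 itch.

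**Prohibited therapy.** Protocol 6.6.3 bars topical corticosteroids, tacrolimus, pimecrolimus, PDE4 inhibitors, other topical AD agents (bland emollients excepted) and systemic immunosuppressants. Protocol 6.5.2 requires permanent discontinuation in one related case: "Participant presents with a worsening of AD that requires treatment with a prohibited concomitant medication". Protocol 7.1.1 makes that mandatory. It lists other noncompliance among the reasons for which a child may be stopped, after consulting the medical monitor.

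**Analysis of such use.** SAP 6.3 says that deviations such as "the use of prohibited concomitant medications, will be reviewed", with exclusion from the PP population decided case by case before unblinding. SAP 6.6 and Appendix A add a descriptive table, "Summary of Concomitant Therapies for AD During the VC Period".

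**Planning figures.** SAP 3.3: "The sample size calculation is based on the Fisher exact test for the primary efficacy endpoint"; the response rate "is assumed to be 51% and 47% for the active arms" "versus 14% for placebo"; and "Using a 2-sided alpha of 0.025, the sample size will have > 95% power" for each active arm.

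**The concern.** The plan already scores stopping the cream as failure, so it does not simply take every child's observed outcome. Yet a child whose skin cleared with help from a topical corticosteroid, and who kept applying the assigned cream, is scored as a success of that cream. If such use differs between arms, the difference in response rates no longer measures the cream alone. Neither document says whether this is intended. If it is left unstated, the handling could be settled after the sponsor is unblinded at the primary database lock.

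**Working it through.** **1. Follow each type of child through the rules.**

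| Situation before Week 8 | Protocol 10.4.1 | SAP 7.2.2 |
|---|---|---|
| Worsening AD requires a prohibited medication; cream stopped; no Week 8 IGA | Nonresponder | Nonresponder |
| Same, but a Week 8 IGA is recorded and meets IGA-TS | Nonresponder | Read literally, not caught unless the child also leaves the study |
| Prohibited therapy used without such worsening; cream stopped at discretion | Nonresponder | As in the two rows above |
| Prohibited therapy used; cream continued; Week 8 IGA meets IGA-TS | Responder | Responder |

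The last row is the gap. The second row is a separate defect: the SAP joins the missing assessment and the discontinuation with an *and*, which is narrower than the protocol, while SAP 11.1 declares no change from the protocol.

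**2. Look for another analysis that covers it.** Multiple imputation, last observation carried forward and the tipping point (SAP 7.2.4.2 to 7.2.4.4) deal with missing values. The longitudinal model (7.2.4.1) uses observed IGA-TS. The PP rerun drops such children only if the review so decides.

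**3. Reproduce the planned power.** Inputs: 126 per active arm and 63 on vehicle (Protocol Table 2), rates of 51%, 47% and 14%, two-sided Fisher exact test at 0.025. Full enumeration gives 99.9% (51% v 14%) and 99.5% (47% v 14%), in line with the stated figure of more than 95%. The planned differences are 51 − 14 = 37 and 47 − 14 = 33 points.

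**4. Size of the shift.** Let u be the share of an arm that uses prohibited therapy and stays on cream, and r the share of those users who meet IGA-TS but would otherwise fail. Scoring them on observed IGA adds u × r to that arm's rate, so

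shrinkage = r × (u_vehicle − u_active).

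Neither u nor r is in the documents. Assume u_vehicle of 5 to 15% (about 3 to 9 of 63), u_active of 1 to 3% (about 1 to 4 of 126) and r of 30 to 60%.

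- Smallest: 0.30 × (5 − 3) = 0.6 points.
- Largest: 0.60 × (15 − 1) = 8.4 points.
- Use higher on active, for example 10% v 5% with r = 50%: 0.50 × (5 − 10) = −2.5, so the difference grows by 2.5 points.

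**5. Power after the shift.** Same Fisher calculation, taking the planning rates to count users as nonresponders.

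| Use, active / vehicle | r | Difference, 1.5% / 0.75% | Power, 1.5% / 0.75% |
|---|---|---|---|
| 2% / 5% | 30% | 36.1 / 32.1 | 99.8% / 99.0% |
| 5% / 10% | 50% | 34.5 / 30.5 | 99.3% / 97.4% |
| 1% / 15% | 60% | 28.6 / 24.6 | 94.0% / 85.0% |
| 5% / 20% | 50% | 29.5 / 25.5 | 95.1% / 87.0% |

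The third row is the 8.4-point corner of step 4: vehicle 14 + 0.60 × 15 = 23.0%, active 51.6% and 47.6%. The last row goes beyond the assumed vehicle range.

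**The case against.** **Counting observed outcomes is legitimate.** Analysing by assigned arm whatever else was used is a recognised treatment-policy choice and is compatible with the ITT definition. This stands as a possible intention. But neither document states it, and scoring discontinuation as failure shows that the plan is not treatment policy throughout.

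**Conduct safeguards exist.** A reader might infer that use outside Protocol 6.5.2 leads to nothing but PP review. It does not. Children are asked about other topical, systemic and over-the-counter products (Protocol 6.4), noncompliance goes to the medical monitor (7.1.1), and withdrawal for compliance is possible (7.2). These steps reduce the number affected. They are discretionary, and none sets the Week 8 score of a child who stays on cream.

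**The use rates may be too high.** Protocol 6.5.2 removes the most obvious route. The nearest figure in the documents is AD-worsening adverse events in the pooled adolescent and adult studies: 4.4% on vehicle against 0.2% and 0.4% on active (Protocol Table 5). That is an event rate, not a rate of medication use. If residual use were as frequent, the shrinkage would be between 0.30 × (4.4 − 0.4) = 1.2 and 0.60 × (4.4 − 0.2) = 2.5 points. The upper end of the range in the working should be read with that in mind.

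**The reference point is uncertain.** The planning rates come from two earlier studies, and the documents do not say how those studies scored users. If on observed IGA, 37 and 33 already include some of the effect.

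**The table of concomitant AD therapies.** A reader might take it as evidence that prohibited use is expected. It is flagged as a standard table and could be filled by permitted measures such as emollients or bleach baths, so it shows only that the data will be available.

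**Conclusion.** The gap is real on the text of both documents: use of a therapy barred by Protocol 6.6.3 does not by itself make a child a nonresponder, for IGA-TS or for Week 8 itch. The narrower SAP wording on discontinuation weakens even the route through Protocol 6.5.2.

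Its size rests wholly on assumed use and response. Within the stated ranges the difference shrinks by 0.6 to 8.4 points from 37 and 33. It would be tempting to call the bias conservative. The documents do not support a fixed direction: more use on vehicle shrinks the difference, more on active enlarges it, and a systemic corticosteroid given for another condition has no evident reason to differ by arm. Nor do they support saying that the primary test is at risk. Power falls below 93% only for the 0.75% arm and only with heavy vehicle use and high response among users (85% and 87% in the working). The matter is the size and meaning of the estimate, and it should be settled before unblinding.

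**What to change.** In SAP 7.2.2, and by reference in 7.3.2 for Week 8 itch:

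1. Define as nonresponders the participants with confirmed use, after Day 1 and before the Week 8 assessment, of a Protocol 6.6.3 therapy capable of affecting AD. Identify agents and timing in a blinded review before the primary database lock. Do not apply for this purpose the SAP 4.2.2 default that treats a therapy as concomitant unless it is unequivocally not. With an incomplete stop date, that default could turn a treatment washed out before entry into a Week 8 failure.
2. Align the discontinuation wording with Protocol 10.4.1, so that stopping study treatment before Week 8 is sufficient whether or not a Week 8 IGA exists.
3. Add a sensitivity analysis on observed Week 8 outcomes regardless of such use.

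Protocol 6.6.2 restricts only the timing of other topical treatments applied to active AD lesions, while 6.6.3 bars other topical agents for AD. The two passages must be reconciled before the list can be coded.

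The cost is SAP wording and a blinded medication review. Medications are already recorded (Protocol 6.6) and coded (SAP 6.6), so no new data are needed. Response rates may come out slightly lower, and agent and timing limits are needed so that trivial or pre-study use does not make a true responder a failure.
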